#### 6.1.7.1 Treatment Procedure

Prior to injection, the treatment area should be cleaned with a suitable antiseptic solution. An appropriately sized syringe and needle (e.g., 30-33 gauge needle) should be used to administer treatment.

At baseline, subjects will be randomized to receive treatment with QM1114-DP or placebo. Each treatment includes five intramuscular (IM) injections of equal volume (0.1 mL) administered at 5 injection sites in the glabellar region (0.5 mL in total). The injections should commence in the procerus muscle followed by the corrugator supercilii muscles on each side, moving outwards from the median. All injections should be approximately 1 cm above the upper orbital rim and internal to the mid-pupillary lines (Figure 2).

In order to minimize risks of regional effect of the neurotoxin (e.g., eyelid ptosis), the investigator should use one thumb to apply pressure on the upper orbital rim while injecting. It is recommended that injection is not closer than 1 cm above the central eyebrow or the bony supraorbital ridge. Moreover, the tip and bevel of the needle should always be pointed away from the study subject.

#### Figure 2 Injection Sites for Treating Glabellar Lines

### 6.1.7.2 Post-treatment Care

Following treatment administration, subjects will be monitored at the study center for 30 minutes.

Subjects will be instructed to avoid applying pressure, rubbing or massaging the treated area, or lying face down for 4 hours after treatment.

### 6.1.7.3 Treatment Regimen

Each subject will receive a single treatment with QM1114-DP or placebo at the baseline visit.

The treatments investigated in this study are:

- 50 U of QM1114-DP (0.5 mL total injection volume/0.1 mL per injection point)
- Placebo

# 6.2 Study Products(s) Packaging and Labeling

QM1114-DP and placebo are manufactured under aseptic conditions.

The labels will be printed in English. The text of the label will detail the information requested by Good Manufacturing Practice and local regulations, and at a minimum include the protocol number, storage conditions, and an investigational test article disclaimer ("Caution: New Drug - Limited by Federal (or United States) law to investigational use.")

CONFIDENTIAL Page 39 of 84

#### 6.3 Supplies Management

#### 6.3.1 Accountability

Upon receipt of the study product(s), the Investigator or designee will maintain accurate records of the study product(s) delivery to the clinical study center, the inventory at the clinical study center, the use by each subject, the reconciliation of all study product(s) received from the Sponsor's designee, and the return to the Sponsor's designee for disposal of unused study product(s).

All study product(s) sent to the Investigator/Institution will be accounted for and no unauthorized use is permitted.

#### 6.3.2 Storage of Study Product(s)

Study product(s) must be stored in a safe and secure area with restricted access, under the storage conditions specified by the Sponsor (see Table 3).

### 6.3.3 Dispensing and Return

All study product(s) must be inventoried and a record of the dispensing for each subject must be appropriately documented. Any dispensing errors must be reported to the Sponsor/CRO and properly documented.

In the event of early termination/suspension of the clinical study, a rapid recall of study product(s) will be initiated.

Unused or expired study product will be returned for destruction to the Sponsor representative at time points approved by the Sponsor.

### 6.3.4 Treatment Compliance Management and Record

The treatment is an injection administered by the Investigator. Details of the injection procedure will be recorded in the eCRF and subject source documents. No other measurements of treatment compliance will be made.

#### 6.3.5 Dose Modification

Dose modifications are not permitted.

### 6.3.6 Product Quality Complaints

Product Quality complaints (PQCs) should be reported to the Safety e-mail listed in Section 0. A PQC is an external judgement presuming a quality defect of a product; quality issue for a product

CONFIDENTIAL Page 40 of 84

**MA-39956** 

relating to its presentation or use, identified by a subject, a practitioner or Investigator site personnel, a distributor, or anyone else involved in clinical supplies handling. Examples may include but are not limited to appearance issues, odor, damaged stoppers, low fills, and foreign matter in the product. These complaints may or may not represent a potential risk to the subject. A PQC form must be completed by the study center personnel and forwarded to the Sponsor or designee within 24 hours of awareness. Affected study product should be guarantined, and not used, until further notice by the Sponsor.

Additional contact details are provided in the Investigator's site file.

#### 6.4 Blinding

This is a double-blind study in which neither the Investigator, sub-Investigator, study staff, nor the subject will know the subject's study product assignment (i.e., QM1114-DP or placebo). Placebo is identical in appearance to QM1114-DP but contains no active drug substance.

Subjects will be randomized at baseline to either treatment with QM1114-DP or placebo. In order to maintain the blind, the study products, QM1114-DP and placebo, will be supplied in identical vials, each with a unique number on the vial label. Both QM1114-DP and placebo will be administered in exactly the same way.

An un-blinded statistician will generate the randomization schedule; however, he/she will not be involved in any other aspect of the study prior to database lock.

The Sponsor's staff or designees directly involved in clinical operations management, data management, and statistical evaluation of the study will remain blinded until the database is locked, unless emergency unblinding is required.

#### 6.4.1 Verification of Blinding

The Sponsor's staff or designees will assess and verify maintenance of the study blind during the study through routine monitoring visits.

#### 6.4.2 **Unblinding During the Clinical Study**

Emergency un-blinding during the clinical study may be required for therapeutic or for regulatory reasons (for expedited safety reporting).

A blind-break system will be available for Investigators. In such an emergency, the Investigator will only break the blind for the subject involved.

The Investigator must notify the Sponsor immediately in the event of such an emergency (see contact details in Section 7.2.6.2.2). If possible, the Investigator should notify the Sponsor before breaking the blind in order to discuss this decision with the Sponsor. The Investigator is required to document each case of emergency unblinding and inform the Sponsor immediately.

> CONFIDENTIAL Page 41 of 84

#### 7. CLINICAL STUDY ASSESSMENT

#### 7.1 **Efficacy Assessments**

#### 7.1.1 4-point Photographic Scale of Glabellar Line Severity: Investigator Live Assessment (GL-ILA)

The validated Investigator 4-point Photographic Scale of Glabellar Line Severity (Appendix 1) includes two grading systems: one for Investigator live assessments at maximum frown,

. The scale represents the severity of GL from none (grade 0), mild (grade 1), moderate (grade 2) to severe (grade 3). Each grade is also depicted by an individual photograph and a descriptive text. The Investigators will be trained on the use of the 4-point Photographic Scale.

The Investigators will use the 4-point Photographic Scales for direct, live comparison with the subject's face at CCI at maximum frown at screening, baseline (prior to treatment), and at all post-treatment visits.

#### 7.1.2 Static 4-point Categorical Scale of Glabellar Line Severity: Subject Live Assessment (GL-SLA)

Subjects will make their assessment of glabellar line severity independently of the Investigator's assessment. Subjects will be asked to evaluate their GL at maximum frown at screening, baseline (prior to treatment), and at all post-treatment visits using the following Static 4-Point Categorical Scale.

Grade	Severity of Glabellar Lines	Description
0	No wrinkles	Smooth skin
1	Mild wrinkles	Fairly smooth skin
2	Moderate wrinkles	Frown lines
3	Severe wrinkles	Deep frown lines

CONFIDENTIAL Page 43 of 84

### 7.2 Safety Assessments

Safety assessments will be conducted for all subjects at the time points indicated in Schedule of Assessments (Table 2). Safety parameters include an evaluation of AEs, FPE, vital signs, ECG, laboratory safety tests (chemistry and hematology), and neutralizing antibody production.

#### 7.2.1 Focused Physical Examination (FPE)

At the time points indicated in the Schedule of Assessments (Table 2), the Investigator or designee will perform a physical examination of the subject that includes the face, head, and neck. Further details are provided in Appendix 5.

Post-baseline, the signs and symptoms will also be monitored via physical examination of face, head, and neck to evaluate local effect of toxin. In addition, general physical examination to evaluate the

CONFIDENTIAL Page 44 of 84 remote spread events will be conducted. The list of remote spread of toxin events is considered while doing clinical evaluations based on subject's symptoms and signs (Appendix 6). Directed questioning and examination will then be performed as appropriate.

The Investigator may choose to investigate any other sign that he/she observes during the physical examination. Abnormalities noted pre-injection, i.e. at the screening/baseline visits, should be recorded as medical history and abnormalities noted post-injection should be recorded as AEs.

# 7.2.2 Vital Signs

Evaluation of vital signs shall be performed after approximately 10 minutes rest in the sitting position. It shall include measurement of systolic and diastolic blood pressure, heart rate, and respiratory rate. Vital signs will be taken prior to any blood draw, excluding post-treatment measurements on Day 0.

All abnormal values at the baseline visit identified as clinically significant by the Investigator shall be recorded in the Medical History form.

For any clinically significant changes from the baseline visit, an AE is to be recorded.

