### SCHEDULE OF ASSESSMENTS

#### Table 2Schedule of Assessments

1  month = 4  weeks/28  days	Visit 1	Visit 2	Visit 3	Visit 4	Visit 5	Visit 6	Visit 7	Visit 8	Visit 9	Visit 10
All visit windows are calculated from Baseline/Day 0	Screening 	Baseline/Day 01	Day 7	Day 14	Month 1	Month 2	Month 3	Month 4	Month 5	Month 6/ET 
		(mithin 2 much a floor	(114)		(15.1.)					(15.1)
		(within 2 weeks after screening)	(±1 day)	$(\pm 3 \text{ days})$	(±5 days)					
Informed Consent	Х									
Demographic Data  including, Fitzpatrick skin type, medical										
history & concurrent diseases, previous facial	Х									
treatments/procedures (toxin naïve/non-toxin naïve)										
Inclusion /Exclusion Criteria	Х	$X^4$								
Concomitant Therapies/ Procedures	Х	X 	Х	Х	Х	Х	Х	Х	Х	Х
Adverse Events	Х	X 	Х	Х	Х	Х	Х	Х	Х	Х
Urine Pregnancy Test 	Х	$X^4$								Х
Vital Signs (blood pressure, heart rate, and respiratory rate) 		X 	Х	Х	Х					Х
ECG		$X^4$			Х					Х
Blood sample clinical chemistry and hematology		$X^4$								Х
Blood sample for serum antibody testing		$X^4$			Х					Х
ILA of GL Severity	Х	$X^4$	Х	Х	Х	X	Х	Х	Х	X
Focused Physical Examination (face, head, neck) 	Х	$X^4$	Х	Х	Х					X
Photography		$X^4$	Х	Х	Х	X	Х	Х	Х	X
Randomization		$X^4$								
Treatment		X 								
CCI										
Subject Assessments										
SLA of GL Severity 	Х	$X^4$	Х	Х	Х	Х	Х	Х	Х	Х
CCI										

1. Screening and baseline visits may be on the same day. If completed on the same day, only perform study assessments once (i.e., PE, UPT, SLA, ILA, AE, concomitant therapies/procedures, inclusion/exclusion review).

- 2. If the subject withdraws before the final visit the assessments at Month 6/ET should be completed, if possible.
- 3. Includes date of birth, gender, race, ethnicity, height, weight.
- 4. To be performed before treatment.
- 5. Performed before treatment and post-treatment.
- 6. Females of childbearing potential
- 7. Vital signs are taken seated after 10 minutes rest. Vital signs are taken prior to any blood draw (excluding post-treatment measurements on Day 0).
- 8. Post-baseline, events suggestive of remote spread of toxin are also considered while doing clinical evaluations based on the subject's symptoms and signs. Directed questioning and examination will then be performed as appropriate.

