### 7.2.6.1 Definitions

### 7.2.6.1.1 Adverse Events (AE)

According to ICH E2A, an AE is any untoward medical occurrence in a patient or a clinical investigation subject administered a pharmaceutical product and which does not necessarily have a causal relationship with this treatment. An AE can therefore be any unfavorable and unintended sign (including an abnormal laboratory finding), symptom, or disease temporally associated with the use of a medicinal (investigational) product, whether or not related to the medicinal (investigational) product.

Thus, any new sign, symptom or disease, or any clinically significant worsening of an existing sign, symptom or disease (including new episodes of a chronic disease [e.g., hay fever, allergy]) compared to the condition at the first visit, should be considered as an AE. Lack of efficacy is not considered as an AE.

Notes:

- There should be an attempt to report a diagnosis rather than the signs, symptoms or abnormal laboratory values associated with the report of an AE. However, a diagnosis should be reported only if, in the Investigator's judgment, it is relatively certain. Otherwise, symptoms, signs, or laboratory values should be used to describe the AE.
- Pregnancy is not to be considered as an AE; however, is an important medical event that must be monitored as described in Section 7.2.6.2.3.
- The effects of all BoNT products may spread from the area of injection to produce symptoms consistent with BoNT effects. These symptoms have been reported hours to weeks after injection. Remote spread of toxin that affects swallowing and breathing can be life threatening, and there have been reports of death. The risk of symptoms is increased in subjects who have underlying conditions (e.g. disorders of the neuromuscular junction) that would predispose them to these symptoms. BoNT is contraindicated in individuals with known hypersensitivity to any BoNT preparation or to any of the components in the formulation.

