- 16. For all subjects, enter appropriate data into the eCRF; the SIN should have been assigned via the eCRF system at the screening visit.
- 17. For subjects who meet all eligibility requirements, the Investigator or designee will receive notification of the subject's kit number/randomization assignment once all required data is entered into the eCRF. The Investigator or designee should prepare the assigned treatment accordingly and complete the required documentation and eCRF (Section 6.1.7).
- 18. Prior to injection, clean the subject's treatment area with a suitable antiseptic solution.
- 19. The Investigator will administer the assigned treatment. See Section 6.1.7.1 for injection technique and treatment procedure requirements. Following treatment administration, subjects will be monitored at the study center for 30 minutes (Section 6.1.7.2).
- 20. Obtain the subject's post-treatment vital signs (blood pressure, heart rate, and respiratory rate). Vital signs are to be taken seated after 10 minutes rest (Section 7.2.2).
- 21.
- 22. Ask the subject about AEs using an open-ended question. Record all events, as appropriate, on the corresponding eCRF form(s).
- 23. Record post-treatment concomitant therapies/procedures.
- 24. Schedule the next visit (Day  $7 \pm 1$  day).

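### The vital-signs recording rule splits findings by visit although the baseline visit spans the injection, so it conflicts with the protocol's AE and TEAE definitions for abnormalities first seen after dosing on Day 0

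*Protocol*

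**What the plan says.** Protocol section 7.2.2 gives two recording rules for vital signs. The first is "All abnormal values at the baseline visit identified as clinically significant by the Investigator shall be recorded in the Medical History form". The second is "For any clinically significant changes from the baseline visit, an AE is to be recorded". Neither refers to the injection.

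The baseline visit contains two sets of vital signs. In Table 2, footnote 5 applies to vital signs at Visit 2 and reads "Performed before treatment and post-treatment". In section 8.1.2 the injection is step 19, and step 20 begins "Obtain the subject's post-treatment vital signs (blood pressure, heart rate, and respiratory rate". Section 7.2.2 itself acknowledges the second reading when it deals with the order of procedures: "Vital signs will be taken prior to any blood draw, excluding post-treatment measurements on Day 0".

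The general safety rules are tied to treatment, or to the subject's condition at the first visit. Section 7.2.6.1.1 treats as an AE "any new sign, symptom or disease, or any clinically significant worsening of an existing sign, symptom or disease". Section 7.2.6.1.2 defines a TEAE as an event that emerges or worsens relative to the state before treatment. Sections 7.2.6.1.5 and 7.2.6.2.1 run AE collection from consent to the end of participation. Step 22 of section 8.1.2, two steps after the post-treatment vital signs, says "Ask the subject about AEs using an open-ended question. Record all events, as appropriate, on the corresponding eCRF form(s".

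For the focused physical examination, section 7.2.1 divides findings at the injection: those found before it are medical history, while "abnormalities noted post-injection should be recorded as AEs".

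**The concern.** A rule that decides between medical history and AE should divide findings at the start of treatment. Section 7.2.2 divides them by visit, and this visit lies on both sides of the injection. A site that applies the vital-signs rule as written would enter a post-injection change in blood pressure, heart rate or respiratory rate on a form meant for conditions the subject already had.

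Two consequences follow. First, incidence and severity of TEAEs is a listed safety endpoint (section 2.1.4), and a finding entered only as medical history does not reach the TEAE tables. Second, such an entry makes the finding look as if it was present before treatment. If the abnormality persists to Day 7, a site could reasonably conclude that nothing has changed since the baseline visit and record no AE then either.

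The Day 0 post-treatment reading is the only scheduled post-dose vital-sign measurement before Day 7, so no later reading replaces it for an acute change.

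**Working it through.** No arithmetic applies, and the protocol gives no figure to reproduce. The check sets the rules against each other for the situations that can arise on Day 0. Table 2 schedules no vital signs at screening, so the pre-injection Day 0 reading is the only scheduled reading before treatment.

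| Situation | Section 7.2.2, read literally | AE and TEAE definitions (7.2.6.1.1, 7.2.6.1.2) | Conflict? |
|---|---|---|---|
| A. Abnormal before injection, unchanged after | Medical History | Not an AE | No |
| B. Normal before, clinically significant abnormality after | Medical History; AE sentence unclear | AE, treatment-emergent | Yes |
| C. Abnormal before, clinically significantly worse after | Medical History; AE sentence unclear | AE, treatment-emergent | Yes |
| D. As B, still present at Day 7 | AE if compared with the pre-injection reading, no AE if compared with the post-injection reading | AE, treatment-emergent | Depends on the reference reading |

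**Why B and C conflict.** The Medical History sentence covers all clinically significant abnormal values at the visit, and the post-injection reading is a procedure of that visit. The AE sentence covers changes from the visit. A change between two readings within the visit is not clearly a change from it.

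**Why D is undetermined.** With two readings at the reference visit, section 7.2.2 does not say which one a later value is compared with.

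**Are the neighboring rules affected?** The other Medical History rules do not raise this problem:
- The baseline ECG is taken before treatment (section 7.2.3).
- The baseline blood samples are taken before treatment (section 7.2.4).
- The Day 0 focused physical examination is before treatment (Table 2, footnote 4), and its rule divides at the injection in any case (section 7.2.1).

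Of these assessments, only vital signs combine a post-dose reading at the baseline visit with a rule defined by visit.

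**How many subjects?** The planned number treated is 225 + 75 = 300, and each is due to have the Day 0 post-treatment reading. That counts readings, not events. The protocol gives no rate of clinically significant post-injection abnormalities, so the number of misfiled findings cannot be estimated.

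**The case against.** A reader might infer that acute post-dose abnormalities on Day 0 would not be recorded as AEs at all, or that every one of them would be lost. The protocol does not support that:
- The AE and TEAE definitions cover these findings, and they arise within the AE collection period.
- Table 2 marks AEs at Visit 2 with the same before-and-after footnote as vital signs, and step 22 of section 8.1.2 has AEs asked about and recorded after the post-treatment reading. No post-treatment step mentions medical history.
- Section 7.2.1 uses the screening and baseline visits as shorthand for the period before injection. If section 7.2.2 borrows that shorthand, many investigators would read it in the harmless sense.

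These points stand, and they reduce the finding to conflicting instructions. They do not remove it. Section 7.2.2 is the specific rule for vital signs, so site staff may well apply it ahead of general definitions. The step 22 enquiry is an open question to the subject and may not bring out a change that causes no symptoms.

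Other strong readings should also be set aside:
- Section 7.2.1 governs examination findings, not vital signs. It shows the intended dividing line but is not a contradictory instruction for the same data.
- The post-treatment reading is not the only check on acute effects. Subjects are also monitored for 30 minutes and asked about AEs.
- Bradycardia and respiratory events appear in Appendix 6, but section 7.2.6.1.1 places spread symptoms hours to weeks after injection, and vital signs and examinations follow at Day 7, Day 14 and Month 1. A same-visit reading is not the main way to detect them.
- The data are not lost. Vital signs are summarized (section 9.1.3.2) and all data are listed (section 9.1.3), whichever form the site uses.
- The choice of Day 0 reading as baseline for the change-from-baseline summaries is a data convention that section 9.1 leaves to the SAP. It is not counted as a fault here.

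**Conclusion.** The point holds as a conflict between instructions. For a clinically significant vital-sign abnormality that first appears or worsens after injection on Day 0, section 7.2.2 read literally points to medical history, while the general definitions and the visit procedures point to an AE. The effect is a risk of misclassification, inconsistent recording between up to 15 centers and some under-counting of acute Day 0 TEAEs.

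The size cannot be stated. It depends on how often such abnormalities occur, which the protocol does not give, and on how many sites follow the specific rule rather than the general definitions. Both may be small. The conclusion rests on the literal reading of section 7.2.2 being one that a site could reasonably adopt. It does not require that all sites adopt it. The primary and secondary efficacy analyses, the sample size and the type I error are not affected. The point still merits correction because it bears on a listed safety endpoint and the remedy is a matter of wording.

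**What to change.** Amend section 7.2.2 in two places:
1. Limit the Medical History sentence to clinically significant abnormal values obtained before treatment.
2. State that a clinically significant change from the pre-treatment reading is recorded as an AE, including when it is seen at the post-treatment reading on Day 0.

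This brings vital signs into line with the division at the injection in section 7.2.1 and with the AE and TEAE definitions in sections 7.2.6.1.1 and 7.2.6.1.2. A matching line in the eCRF completion guideline would help sites apply it uniformly. The baseline reading for the summary tables can be named in the SAP.

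The cost is a short wording amendment, with no new procedure, visit or measurement. The one foreseeable downside is that a few more AEs may be recorded.
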